Data collected during the eligibility screening and enrollment of Cohort A1 and A2 will be compared to examine changes in HIV prevalence, prevalence of circumcision among men, sexual risk behavior, exposure to sexual risk reduction campaigns; among those HIV infected, self-reported use of ART, engagement in care, and viral load level; and to examine the association of baseline demographic characteristics with HIV prevalence.

[figure not shown]
Figure 4. Longer-term prospective cohorts

Primary Objective 2a & 2b and Secondary Objective 4b & 4c

Data collected during enrollment and follow up of men 25-34 years old and women 18-24 years old enrolled in Cohort B will be used to estimate HIV incidence rates and describe sexual risk behaviors for an additional 6-18 months after completion of MC ASI.

[figure not shown]
Figure 5. All three cohorts

Primary Objective 3 and Secondary Objective 7

HIV incidence rates in men in all cohorts described above will be compared by the circumcision status of the men. The annual number of HIV infections averted among men due to circumcision calculated.

Figure 6. Cross-Sectional Cohort C

Secondary Objective 8 and 9

Data collected from HIV-infected men and women will be used to estimate CD4 count distribution, viral load distribution, and the proportion who have a CD4 count <350 cells/mm³ and who report no current ART use.

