5.3.3 Longer-term Longitudinal cohort (Cohort B)

- Inclusion criteria
 - Completed 12- month follow-up in Cohort A2
 - For males, reported age between 25 – 34 years; for female, reported age between 18 – 24 years
 - Confirmed HIV-negative by Swazi rapid HIV test algorithm
 - Willing to adhere and undergo all study visits and procedures
 - Able to provide answers to the study questionnaires administered in either English or siSwati
 - Able to provide consent in either English or siSwati

- Exclusion criteria
 - Stated intent to leave Swaziland indefinitely for work or any other reason in the next 6 months

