7.2 Sampling, including sample size and statistical power

A nationally-representative sample of men and women will be identified for both the baseline and post-intervention surveys and cohorts via a two-stage cluster-based sampling of 'enumeration areas' and households. Enumeration areas are sampling points defined by the 2007 Swaziland Population and Housing Census. A total of approximately 575 enumerations areas will be drawn from the census sample frame of all 2000 enumeration areas with a probability of selection proportional to the number of households within the enumeration area. The enumeration areas in urban versus rural areas will be proportional to the urban versus rural distribution of the population. Between November 2010 and May 2011, staff will conduct an exhaustive listing of households within each sampled enumeration area. During household listing, study staff will use Global Positioning Systems (GPS) receiver to record the geographic coordinates of each cluster and household. In the pre-MCASI cohort, approximately 14,884 households will be sampled, and 12,301 households will participate in the study. From these households we expect to identify, recruit, screen, and enroll a sample size of 5,823 men and approximately 7,106 women in the first seroincidence cohort (Cohort A1). In the post-MC ASI cohort, approximately 15,758 households will be sampled, and 13,024 households will participate in the study. From these households we expect to identify, recruit, screen, and enroll a sample size of 6,165 men and approximately 7,524 women in the second seroincidence cohort (Cohort A2). From Cohort A2, we expect approximately 25% of the men will be 25-34 years old, and 29% of the women will be 18-24 years old, yielding the longer, 6 month longitudinal cohorts of 1,541 men and 2,182 women (Cohort B).

Statistical power calculations for primary objectives are included as Appendix P.

Primary Objective #1a:

To estimate HIV incidence in household-based representative sample of men at baseline and post MC ASI. (Cohort A1 vs A2)

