The sample size for the men’s Cohort A1 is 5,823 and for Cohort A2 is 6,165. Each person enrolled in Cohort A1 contributes 6 months of follow-up and in Cohort A2, each contributes 12 months of follow-up. The sample size is chosen to achieve sufficient “effective” person years to achieve 80% power to detect a 45% reduction in ratio of infection rates, assuming a Poisson distribution in each cohort of number of seroconversion events in total accumulated person years.

Note: Very similar sample sizes result from comparison of binomial probabilities of the proportion of the cohort infected in the pre vs. post MC ASI cohorts, provided exact methods are used. Poisson analysis is planned to accommodate varying lengths of follow-up time in the follow-up cohort.

- Men. The total number of person-years required to detect a 45% reduction in the HIV incidence rate from 2.0 per 100 person years (approximated baseline rate) to 1.1 per 100 person years (post-intervention) with a 1:2 ratio of person years in the two cohorts is 6,288. With a design effect of 1.25 and loss to follow-up of 10% and 15% in the pre- and post-MC ASI this yields a sample size of 5,823 men followed for 6 months and 6,165 men followed for 12 months in Cohort A1 and Cohort A2 respectively. (See Tables 1 and 2)

Table 1:

Effective person years required to detect 30-60% difference between infection rates with 6 month follow-up in Cohort A1, 12 month follow-up in Cohort A2, for two sided alpha of 0.05, and 80% power. Wald test statistic for slope in Poisson Regression, under assumption of simple random sample.				
λ_1	λ_2	Ratio λ_2/λ_1	Total Effective ¹ Person Years (Both serocohorts combined)	
0.0200	0.0140	0.70	15865	
0.0200	0.0130	0.65	11224	
0.0200	0.0120	0.60	8272	
0.0200	0.0110	0.55	6289	
0.0200	0.0100	0.50	4901	
0.0200	0.0090	0.45	3898	
0.0200	0.0080	0.40	3155	
0.0300	0.0210	0.70	10577	
0.0300	0.0195	0.65	7483	
0.0300	0.0180	0.60	5514	
0.0300	0.0165	0.55	4192	
0.0300	0.0150	0.50	3267	
0.0300	0.0135	0.45	2599	
0.0300	0.0120	0.40	2103	

¹Effective person years assume a simple random sample.

Number of households

The number of households required to achieve the effective sample size is shown in Table 2. The derivation of each of the adjustment factors is as follows:

- Design Effect: Design effect for HIV in men ages 15-49 of 1.25, and the DEFT of 1.32, are both based on the 2006-07 DHS.
- Household adjustment:

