From the sample of 5823 men in the pre-MC-ASI cohort (Cohort Aa), we expect 25% of the men to be aged 25-34, a sample of 1456. From the sample of 6,165 men in the post-ASI cohort (Cohort A2), we expect 25% of the men to be aged 25-34, a sample of 1,541. If we compare the seroincidence in the 26-34 year old men 6 months prior to MC ASI to the seroincidence in the 18 months period (24-42 months following the end of the pre-MC-ASI cohort), we would have ~80% power to detect a 50% reduction in HIV seroincidence, assuming a pre-MC-ASI seroincidence of 5.0 per 100 person years, after accounting for lost to follow-up of 12% per year, and a design effect of 1.25 in each cohort

Primary Objective #2b

To estimate HIV incidence rates in the highest risk age subsets of women ages 18-24 in the household-based, nationally representative sample for an additional 6-18 months after the MC ASI completion (Cohort B).

From the sample of 7524 women in the post-ASI cohort (Cohort A2), we expect 29% of the women to be aged 18-24, a sample of approximately 2183. If we compare the seroincidence in the 6 months prior to MC ASI to the seroincidence at 24-42 months following MC ASI, we would have ~80% power to detect a 40% reduction assuming a seroincidence of 6.0 per 100 person years, after accounting for lost to follow-up of 10% per year, and a design effect of 1.25 in each cohort

Primary Objective #3

To estimate HIV incidence of circumcised compared to uncircumcised men in a household-based representative sample of men post- MC ASI (Cohort A2).

The 6165 men in the post-MC ASI cohort (A2) gives 71% power to detect a 55% decrease in the HIV incidence rate ratio between circumcised and uncircumcised men, assuming 80% of the men are circumcised and 20% are uncircumcised (i.e. a ratio of 4:1) and the seroincidence rate in the uncircumcised men is 2.5 per 100 person years, 12% loss to follow-up. If 2/3 of the men are circumcised, the power is increased to 83%. As the comparison will be within the cohort, no adjustment for design effect is assumed.

As the primary objectives capture the most important scientific objectives of importance, power consideration are only given for these objectives.

Secondary Objectives #8, and #9

- 8) To describe the concurrent CD4 count and viral load distributions in a nationally representative sample of HIV-infected men and women ages 18-49, in the context

of ART use.

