8.1.3 Analysis of primary objectives: Comparison of HIV incidence rates

Primary Objectives 1a & 1b and 2a & 2b

Comparisons of rates of seroincidence in the pre vs post MC ASI will compare incidence rate ratios assuming a Poisson distribution of seroconversions in the follow-up time in each cohort. The HIV seroincidence rates, computed as the total number of seroconversions divided by the total number of person years, adjusted by sampling weights to achieve a population, age, and gender based estimate of seroincidence will be compared in the pre vs post MC ASI in Cohorts A1 and A2. The statistic is the Wald test statistic for the slope of a Poisson regression with a binary covariate for pre vs post MC ASI. Cohorts A1 and A2 are based on independent samples. Each is intended to be representative of the contemporary Swaziland population, thus the sample weighting in each cohort will be based on current population estimates. s

For men in the baseline cohort (Cohort A1) who become circumcised between the time of cohort enrollment and follow-up, only person years prior to circumcision will be included in the analysis. All follow-up time from men who are circumcised prior to enrollment, and men who remain uncircumcised at follow-up, will be included. All follow-up time from women will be included.

To account for potential dependence of HIV seroincidence within households a sensitivity analysis using bootstrap resampling techniques will assess the effect of sampling multiple people from each household on the primary analysis.

Sensitivity analyses will be conducted to assess the impact of any population based demographic changes in the HIV-uninfected population between the pre and post MC ASI periods.

Primary Objective 3

Comparisons of rates of seroincidence in the circumcised vs. uncircumcised men in the post-MC ASI male cohorts will compare incidence rate ratios assuming a Poisson distribution of seroconversions in the follow-up time in each group. The HIV seroincidence rates, computed as the total number of seroconversions divided by the total number of person years in each group, adjusted by the cohort sampling weights to achieve a population age-based estimate of seroincidence will be compared in the circumcised vs. uncircumcised men. The statistic is the Wald test statistic for the slope of a Poisson regression with a binary covariate for circumcision.

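### Cohort B's stated sizes omit A2 loss and seroconversion, and the ~80% power for Objective 2 belongs to a window that pools A2 with Cohort B

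*Protocol*

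**What the plan says.** **Size.** Protocol 7.2 gives the age shares for A2: "we expect approximately 25% of the men will be 25-34 years old, and 29% of the women will be 18-24 years old". It multiplies these shares by the full A2 enrolment and reports the product as "yielding the longer, 6 month longitudinal cohorts of 1,541 men and 2,182 women (Cohort B"). Section 1.0 repeats both numbers as the Cohort B sample size.

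**Entry.** Section 5.3.3 lists as an inclusion criterion "Completed 12- month follow-up in Cohort A2", together with a confirmed negative HIV test. Section 6.3.1 likewise recruits only people who are negative at the 12-month A2 visit.

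**Objective 2.** The protocol describes the analysis in three ways:

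- Section 4.0 says that data on the two age groups "enrolled in Cohort B will be used to estimate HIV incidence rates". Section 1.0 defines Cohort B follow-up as coming after A2's 12 months, and 7.1 says Cohort B measures incidence at a further time point.
- Section 7.2 (Primary Objective #2a) gives about 80% power to compare A1's 6 months "to the seroincidence in the 18 months period (24-42 months following the end of the pre-MC-ASI cohort"). The text for #2b uses months 24-42 as well.
- Section 8.1.3, under a heading that covers 1a, 1b, 2a and 2b, says the weighted rates "will be compared in the pre vs post MC ASI in Cohorts A1 and A2". Cohort B is not named.

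**Follow-up length.** Sections 4.0 (enrolment at Month 36, follow-up at Month 42) and 7.2 schedule 6 months for Cohort B. Sections 1.0, 3.1 and 6.3.4 allow 6-18 months.

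**The concern.** The sizes look like plain shares of A2 enrolment, with nothing removed for people who drop out or seroconvert before Cohort B starts. The power statement sits under an objective labelled Cohort B, yet two-thirds of its post-campaign window is A2 time. A reader of 7.2 could therefore expect a larger cohort than the entry rules allow, and could believe that incidence in the additional follow-up is compared with about 80% power. Objective 2 is a primary objective, and the three descriptions of it lead to different estimates with different power.

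**Working it through.** **Inputs from the protocol.**
- A2 enrolled: 6,165 men and 7,524 women (7.2). A1 men aged 25-34: 1,456 (7.2).
- A1 women aged 18-24: 0.29 × 7,106 = 2,061. This is an assumption, because 7.2 gives the 29% share only for A2.
- Completion at 6 and 12 months: men 90% and 85%, women 92% and 88% (7.2). For Objective 2, 7.2 instead uses annual loss of 12% (men) and 10% (women).
- Baseline rates 5.0 and 6.0 per 100 person-years with reductions of 50% and 40%, so post-campaign rates are 2.5 and 3.6. Design effect 1.25 (7.2).
- Test: "The statistic is the Wald test statistic for the slope of a Poisson regression" (8.1.3), and Table 1 is calculated "for two sided alpha of 0.05, and 80% power".

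**Formula.** Power = Φ(|ln RR| / √(1/E1 + 1/E2) − 1.96), where E = rate × person-years / 1.25. Without the division by 1.25 it returns 80.0% for Table 1 (for example 6,289 effective person-years, 2.0 against 1.1 per 100). For Objective 1b it returns 67.7% and 82.0%, where 7.2 states 68% and 82%. It is therefore the protocol's own method.

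**Step 1: the stated sizes.** 0.25 × 6,165 = 1,541 and 0.29 × 7,524 = 2,182. Nothing has been subtracted.

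**Step 2: apply the entry rules.**
- Men: 1,541 × 0.85 × 0.975 = 1,277, or with 12% loss 1,541 × 0.88 × 0.975 = 1,322. That is 17% or 14% below 1,541.
- Women: 2,182 × 0.88 × 0.964 = 1,851, or with 10% loss 2,182 × 0.90 × 0.964 = 1,893. That is 15% or 13% below 2,182.

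**Step 3: reproduce the stated ~80% (A1 against months 24-42).**
- Men: A1 1,456 × 0.5 × 0.94 / 1.25 = 547 person-years, 27.4 events. Post 1,541 × 1.5 × 0.82 / 1.25 = 1,516 person-years, 37.9 events. SE = 0.251, and 0.693 / 0.251 − 1.96 = 0.80, so power is 78.9%.
- Women: A1 783 person-years, 47.0 events. Post 2,182 × 1.5 × 0.85 / 1.25 = 2,226 person-years, 80.1 events. SE = 0.184, power 79.4%.
- If loss is instead applied stage by stage, to A2 and then to Cohort B, at the annual rates, the results are 79.6% and 79.8%.

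**Step 4: A1 against Cohort B's own 6 months.**
- Annual loss rates throughout. Men: 27.4 against 1,322 × 0.5 × 0.94 / 1.25 × 0.025 = 12.4 events, power 52.7%. Women: 47.0 against 1,893 × 0.5 × 0.95 / 1.25 × 0.036 = 25.9 events, power 55.1%.
- Table 2 and 3 completion throughout. Men: 26.2 against 11.5 events, 50.0%. Women: 45.5 against 24.5 events, 53.2%.
- Table completion into Cohort B, then annual loss: 51.7% and 54.5%.
- With the uncorrected sizes of 1,541 and 2,182: 56.9% and 58.8%. The size error alone therefore does not explain the gap.

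**Step 5: other readings.**

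| Contrast with the A1 age subset | Men | Women |
|---|---|---|
| A2 + Cohort B, months 24-42 | 78-80% | 78-80% |
| A2 age subset only | 71-73% | 72-73% |
| Cohort B only, 6 months | 50-53% | 53-55% |
| Cohort B only, 12 months | 67-69% | 69-71% |
| Cohort B only, 18 months | 75-76% | 77% |

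**Precision, if estimation is the aim.** With about 12.0 effective events in men, the 95% limits are 2.5 ×/÷ exp(1.96/√12.0) = 1.4 to 4.4 per 100 person-years. With about 25.3 in women, they are 3.6 ×/÷ exp(1.96/√25.3) = 2.4 to 5.3. Both are for 6 months.

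**The case against.** The ~80% is not a miscalculation. It reproduces for the window that 7.2 states openly, with loss and design effect accounted for. The protocol says the study is powered for Objective 1a, words Objective 2 as estimation, and nowhere claims 80% for Cohort B alone. Section 3.1 does not name Cohort B, and 7.1 gives it the purpose of describing a post-campaign trend, for which the same people's A2 interval is relevant. All of this stands. It does not resolve the conflict, because 1.0, 4.0 and 7.1 present the additional follow-up as Cohort B's purpose, while 8.1.3 leaves Cohort B out under a heading that covers 2a and 2b. An analysis plan can add detail but cannot show which of these the protocol meant.

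The 50-55% also depends on 6 months of follow-up. Within the allowed 6-18 months, power rises to about 75-77%. A flat statement that Cohort B has only about half the needed power would go beyond the text.

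A reader might also infer that the pooled contrast merely repeats Objective 1. It does not: it uses only the high-risk age groups, different baseline rates and added follow-up, although A1 and A2 person-time is shared.

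Finally, a reader might take off women who pass age 24 during A2. The protocol gives no age distribution within the band, so that loss cannot be sized.

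**Conclusion.** The point holds in two parts.

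First, the Cohort B sizes in 1.0 and 7.2 contradict the entry criteria. On the protocol's own assumptions the eligible numbers are about 1,280-1,320 men and 1,850-1,890 women, 13-17% fewer, before any refusal to enrol. No other enrolment total depends on them: 26,618 is the sum of A1 and A2 only (5,823 + 7,106 + 6,165 + 7,524).

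Second, Objective 2 has no single stated contrast. The ~80% is right for A1 against pooled A2 and Cohort B, and should not be read as wrong or as the power of Cohort B's own follow-up. That power is about 50-55% at the scheduled 6 months and stays below 80% even at 18 months.

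The power figures rest on the post-campaign rates implied by 7.2, the design effect of 1.25, the 29% share holding for women in A1, and the women's window meaning study months 24-42, as for the men. Objective 1 is unaffected. The correction should be made, but it does not threaten the main design.

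**What to change.** 1. In 1.0 and 7.2, restate Cohort B as about 1,280-1,320 men and 1,850-1,890 women, and show the A2 completion and seroconversion factors used.
2. Name one contrast for Objective 2 and the Cohort B follow-up length it assumes, and write both identically in 3.1, 7.2 and 8.1.3. There are three workable choices:
   - Keep the A1 age subset against pooled A2 and Cohort B (about 78-80%), stating that the window includes A2 person-time.
   - Use Cohort B only, with power restated for the chosen follow-up length.
   - Label the objective as estimation and give the expected interval width.
3. In 8.1.3, say explicitly how Cohort B person-time enters the analysis of 2a and 2b.

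The cost is wording and restated figures. No participants or visits are added.

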7.0 STATISTICAL CONSIDERATIONS

7.1 Overview of Statistical Considerations

The overall statistical approach follows from the goal of measuring the population effect of the MC ASI. This is achieved by estimating HIV incidence using two nationally representative, household-based samples of the Swaziland population, one before and one after the MC ASI (Cohorts A1 and A2). The study is powered for primary objective # 1a, with at least 80% power to detect a 45% reduction in the HIV seroincidence rate of HIV-uninfected men 18-49 in Swaziland from pre to post-MC ASI.

A longer longitudinal cohort (Cohort B) of the highest risk age group of HIV uninfected men and women from Cohort A2 will measure HIV incidence at an additional time point, at a greater period post- MC ASI campaign.

The two-stage cluster sampling scheme is designed to achieve a nationally representative sample of households. All consenting, eligible HIV uninfected men and women 18-49 will be followed to estimate HIV incidence. Weighted estimation will be used in order to achieve population based estimates of HIV seroincidence, using weights corresponding to the national household sample achieved.

The number of HIV uninfected men is chosen to achieve a nationally representative sample of men to have at least 80% power to detect 45% reduction in the HIV seroincidence rate of HIV uninfected men 18-49 in Swaziland from pre to post-MC ASI. The number of households approached will yield a sample of women from which we can estimate the reduction in HIV seroincidence rate of HIV uninfected women 18-49 in Swaziland from pre to post-MC ASI.

The longer-term longitudinal cohort, Cohort B, will be the subset of men aged 25-34 and women aged 18-25 from Cohort A2. Cohort B will be used to estimate the trend in

seroincidence following the MCASI campaign. Cohort B will also be used to assess the trend in sexual risk behaviors following the MC ASI campaign.

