The household sample of 14,884 and 15,758 in pre- and post- MC-ASI is expected to yield an enrolled cohort of 7106 women and 7,524 in the pre- and post-MC ASI cohorts respectively. (See Table 3)

Number of effective women-years accumulated-

The number of effective women years accumulated from the household sample of 14,884 and 15,758 in pre- and post- MS-ASI is shown in Table 3. The derivation of each of the adjustment factors is as follows:

- Design Effect: Design effect for HIV in women ages 15-49 of 1.25, and the DEFT of 1.32, are both based on the 2006-07 DHS.
- Household adjustment
 - 13% will be vacant/non-contactable, 5% will refuse participation at the household level. Adjustment factor = $1/0.87 \times 0.95 = 1.21$
- Household individual adjustment
 - Women: 105% will have female residents within the eligible age range, 65% will be HIV uninfected, 99% will agree to cohort enrollment, 90% will be contactable, 95% will agree to pre-cohort survey. Adjustment factor = $1/(1.05 \times 0.65 \times 0.99 \times 0.90 \times 0.95) = 1.73$
- Loss to follow-up

Women: 92% and 88% of women will complete follow-up in the 6 and 12 month cohorts, respectively (accounting for loss-to-follow-up, interview/HIV test refusal, data loss, and specimen loss totaling 8% and 12%, respectively). Adjustment factor = $1/0.92 = 1.09$ and $1/0.88 = 1.14$ respectively.

Table 3: Number of enrolled female participants, given sample of 14,884 and 15,758 households in the pre- and post-MC ASI cohort.

Effective number person years	Design effect	Loss to follow-up adjustment	Number Females enrolled	Female household adjustment	Number of households participating	Household adjustment	Number of households sampled
Pre-MC ASIFemale Seroincidence Cohort (Cohort A1) – 6 month follow-up period							
2615	1.25	1.09	7106	1.73	12,301	1.21	14884
Post-MC ASIFemale Seroincidence Cohort (Cohort A2) – 12 month follow-up period							
5297	1.25	1.14	7524	1.73	13,023	1.21	15758

With total effective person years of 7912 in the women, assuming a seroincidence rate of 3.0 per 100 person years, and a sample ratio of 1:2, we have 68% power to detect a 30% reduction in HIV seroincidence and 82% power to detect a 35% reduction in HIV seroincidence.

Primary Objective #2a

To estimate HIV incidence rates in the highest risk age subsets of men ages 25-34 in the household-based, nationally representative sample for an additional 6-18 months after the MC ASI completion (Cohort B).

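### The cited design effect of 1.25 and DEFT of 1.32 cannot describe the same estimate, and the stated 80% power for Objective 1a holds only if 1.25 is the variance ratio

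*Protocol*

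**What the plan says.** Section 7.1 of the protocol says that the study is powered for Objective 1a, "with at least 80% power to detect a 45% reduction in the HIV seroincidence rate" in uninfected men aged 18-49. Section 7.2 derives the person-years "for two sided alpha of 0.05, and 80% power", using the "Wald test statistic for slope in Poisson Regression, under assumption of simple random sample". For a fall from 2.0 to 1.1 per 100 person-years, the total required "with a 1:2 ratio of person years in the two cohorts is 6,288".

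The step from effective person-years to men enrolled uses a clustering allowance, for which section 7.2 gives this source: "Design effect for HIV in men ages 15-49 of 1.25, and the DEFT of 1.32, are both based on the 2006-07 DHS". Under Objective 1b the sentence recurs with only the sex changed: "Design effect for HIV in women ages 15-49 of 1.25, and the DEFT of 1.32, are both based on the 2006-07 DHS".

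Tables 2 and 3 each have a design-effect column, and every entry is 1.25. Section 7.3 again names 1.25 as the allowance for clustering. The figure 1.32 appears nowhere else. For women, section 7.2 concludes: "we have 68% power to detect a 30% reduction in HIV seroincidence and 82% power to detect a 35% reduction". The power statements for Objectives 2a and 2b also rest on 1.25. Objective 3 uses no design effect and is not affected.

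**The concern.** The design effect is the factor by which cluster sampling inflates the variance of an estimate. DEFT is the factor by which it inflates the standard error. One is the square of the other, so a single estimate cannot have a design effect of 1.25 and a DEFT of 1.32. Yet the sentence attaches both to HIV in one sex, one age range and one survey, and then repeats the pair for the other sex. Either a figure is mislabelled or mistranscribed, or the two belong to different groups or estimates.

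The distinction matters because person-years must be multiplied by the variance ratio. If the multiplier should be larger than 1.25, the effective person-years and the power for Objectives 1a, 1b, 2a and 2b are lower than stated. Objective 1a is the only objective on which the study was sized. A null result there would be read against 80% power that may not have existed.

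**Working it through.** **Inputs (protocol, section 7.2).** Rates 0.020 and 0.011 per person-year; two-sided alpha 0.05; 5,823 men for 0.5 year with 10% loss; 6,165 men for 1 year with 15% loss; variance factor D = 1.25.

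**Formulas.** For a Wald test on the log rate ratio:

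- Required: T1 = (1.96 + 0.8416)² × [1/λ1 + 1/(2λ2)] / (ln(λ2/λ1))², with T2 = 2 × T1.
- Power = Φ(|ln(λ2/λ1)| / SE − 1.96), where SE² = 1/(λ1·T1) + 1/(λ2·T2).
- Effective person-years = enrolled × years × (1 − loss) / D.

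**Reproducing the plan.** T1 = 2,096 and T2 = 4,192, total 6,289 (stated 6,288; Table 1 has 6,289). All 14 rows of Table 1 reproduce. Enrolment is 2,096 × 1.25 / 0.90 / 0.5 = 5,822 (stated 5,823) and 4,192 × 1.25 / 0.85 = 6,165 (as stated). Going back, 5,823 × 0.5 × 0.90 = 2,620 and 6,165 × 0.85 = 5,240 person-years; divided by 1.25 these are 2,096 and 4,192. SE = √(0.02385 + 0.02169) = 0.2134, and power = Φ(0.5978/0.2134 − 1.96) = Φ(0.84) = 80.0%. The plan's arithmetic is therefore correct at 1.25.

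**Consistency of the pair.** √1.25 = 1.118, not 1.32. 1.32² = 1.742, not 1.25. 1.25² = 1.5625.

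**Power under each reading, cohorts as planned.** Women use Table 3 (2,615 and 5,297 effective person-years at 1.25, baseline 3.0 per 100), rescaled by 1.25/D.

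| Reading | D | Effective PY, men | Power 1a, 45% reduction | Women, 30% reduction | Women, 35% reduction |
|---|---|---|---|---|---|
| 1.25 is the variance ratio | 1.25 | 6,288 | 80.0% | 67.7% | 82.0% |
| 1.32 is a variance ratio, mislabelled | 1.32 | 5,955 | 77.8% | 65.3% | 79.9% |
| 1.25 is itself a DEFT | 1.5625 | 5,031 | 70.7% | 58.1% | 73.0% |
| DEFT is 1.32 as labelled | 1.742 | 4,511 | 66.0% | 53.5% | 68.3% |

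The first row matches the stated 80%, 68% and 82%. At 1.742, power of 80% is reached only for a reduction of about 52% in men and about 40% in women.

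**Objectives 2a and 2b.** The exact calculation is not given in the text, so I assumed 0.5 year before and 1.5 years after the campaign, with the stated yearly loss applied in proportion.

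- Men (1,456 and 1,541; retention 0.94 and 0.82; 5.0 per 100; 50% reduction): effective person-years at 1.25 are 1,456 × 0.5 × 0.94 / 1.25 = 547 and 1,541 × 1.5 × 0.82 / 1.25 = 1,516. Power is 79%, against about 80% stated, and 65% at 1.742.
- Women (7,106 × 0.29 = 2,061 and 2,182; retention 0.95 and 0.85; 6.0 per 100; 40% reduction): 783 and 2,226. Power is 79%, against about 80% stated, and 65% at 1.742.

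**The case against.** A reader might infer that the true power for Objective 1a is 66%. The documents do not support that. It would require 1.32 to be a genuine DEFT, to belong to the estimate on which the study is powered, and to override the figure that the protocol consistently labels a design effect. The deciding source is the 2006-07 survey, which is not at hand; nor are the contents of Appendix P, where section 7.2 places its power calculations. The mildest failing reading costs only about two percentage points.

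Nor is this an arithmetic slip in Tables 2 and 3. Every step is right at 1.25, and 1.32 is an unused number beside it. If 1.25 is the variance ratio, no power figure changes.

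The strongest point concerns the outcome. Both figures are for HIV in ages 15-49, apparently prevalent infection. The powered outcome is new infection in uninfected adults aged 18-49. With about 575 enumeration areas there are about 5,823/575 = 10.1 enrolled men per area. Ignoring weighting and using D = 1 + (m − 1)ρ, a design effect of 1.25 needs an intra-area correlation of 0.25/9.1 = 0.027, and 1.74 needs 0.74/9.1 = 0.08. Section 7.3 expects only modest clustering within areas, so carrying 1.74 straight into an incidence calculation could understate power.

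All of this stands as a limit on the size of the problem. It does not remove it. The protocol does not defend 1.25 on the ground of incidence; it cites the survey, and the citation contradicts itself. Section 7.3 also warns that new infections may cluster within households more than expected. The planned bootstrap analysis examines that clustering but does not restore power.

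**Conclusion.** The inconsistency is certain, given the usual meaning of DEFT: the two cited figures cannot describe one estimate, for men or for women. Its consequence is conditional. With the planned cohorts and the protocol's own rates, losses and test, Objective 1a has between 66.0% and 80.0% power, depending on how the pair is read. The promise of at least 80% holds only if the variance ratio for incidence is no larger than 1.25, because the design has no margin above it. For women, the ranges are about 54% to 68% for a 30% reduction and 68% to 82% for a 35% reduction. Objectives 2a and 2b run from about 65% to 79%, on the follow-up assumptions stated above. If the design effect for incidence is smaller than the survey figure for HIV status, true power would be higher than the chosen reading implies.

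**What to change.** Check the 2006-07 survey and state, separately for men and women, which figure is the variance ratio and which is the DEFT. Then do one of two things in section 7.2:

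- If 1.25 is the variance ratio, remove 1.32 and add a sentence that justifies 1.25 for HIV incidence in uninfected adults.
- Otherwise, carry the correct variance ratio (DEFT squared where the figure is a DEFT) through Tables 2 and 3, and amend sections 7.1 and 7.3 to match.

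In the second case, keep the sample size and restate the power, or the detectable reduction, for Objectives 1a, 1b, 2a and 2b. In either case, note that the survey factor concerns HIV status in ages 15-49 and that the design effect for incidence may be smaller.

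The cost is one source check and a few corrected figures, with no added participants. If the larger factor stands, the stated power becomes less favourable.
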